6.2 Primary Study Endpoints

Defining an event as performance of ICA when no intervention is necessary, we expect to compare event rates for patients treated with CCTA and FFR-CT, using t-tests and a multivariate, risk adjusted 90 day hazard model with 95% confidence interval. Our null hypothesis is that outcomes will not vary regardless of which testing is used to assess

obstructive disease. Our alternative hypothesis is that evaluation with FFR-CT as oppose to CCTA will change the event rate. We will also correlate noninvasive and invasive FFR studies.

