Methodology	Prospective clinical trial
Study Duration	15 months
Study Center(s)	Single center
Objectives	The purpose of this study is to evaluate the incremental benefit of Fractional Flow Reserve (FFR) derived from Coronary Computed Tomographic Angiography (CCTA) (CT-FFR) compared to CCTA with or without stress testing, using invasive FFR as the gold standard for patients with obstructive disease (> 30% stenosis). This study will also assess the capability of CT-FFR to enhance performance on both negative and positive predictive value for less experienced readers by providing feedback based on CT-FFR evaluation
Number of Subjects	Number of subjects projected for the entire study 572
Diagnosis and Main Inclusion Criteria	Chest Pain and stable angina patients with suspicion of coronary artery disease
Study Product, Dose, Route, Regimen	n/a. The study will assess the capability of measuring fractional flow reserve noninvasively utilizing computers and information provided by routine CCTA studies.
Duration of administration	n/a
Reference therapy	The standard reference will be invasive FFR.
Statistical Methodology	Defining an event as performance of ICA when no intervention is necessary, we expect to compare event rates for patients treated with CCTA and FFR-CT, using t-tests and a multivariate, risk adjusted 90 day hazard model with 95% confidence interval. Our null hypothesis is that outcomes will not vary regardless of which testing is used to assess obstructive disease. Our alternative hypothesis is that evaluation with FFR-CT as oppose to CCTA alone will reduce the event rate. We will assess the comparability of the CCTA readers' readings and compare them to the CT-FFR results and the noninvasive FFR results.

1 Previous Study History

Has this study ever been reviewed and rejected/disapproved by another IRB prior to submission to this IRB?

No Yes – if yes, please explain:

2 Brief Summary of Research

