3.4 Clinical Data to Date

From 1/1/2009 to 3/31/2015 our team introduced and operated a CCTA Chest Pain triage program for low to intermediate risk patients at Stony Brook University Hospital ED and non-emergency outpatient services, the only tertiary care hospital in Suffolk County. Concurrently, we established a registry to monitor patient outcomes for all patients receiving CCTA at Stony Brook Medicine. Our registry contained nearly 15,000 patient CCTA procedures. Our major registry study established the effectiveness of CCTA as an imaging modality for evaluating ED chest pain in a cost efficient manner with a false negative rate less than 1% [5]. However, our registry reflects the poorer positive predictive values documented by other industry studies [6-8].

False positive workup results in the necessity of performing cardiac catheterization on patients at risk for obstructive disease based on assessment with current standard of care (combined screening with CCTA and stress MPI). Reduction in the rate of false positive testing would lead to reduction in risk from invasive procedures and radiation exposure to patients and reduced cost to the health care system.

Several medical institutions currently use HeartFlow CT-FFR as standard of care for evaluating obstructive disease. Generally, the standard of care at these institutions is to refer patients who are 30 to 100 percent obstructed by CCTA and who have reduction of flow \leq to 0.8 that is deemed to be medical significant by the attending cardiologist to Invasive FFR. HeartFlow has reported to us confidentially that this routine use of CT-FFR has resulted in a 54% reduction in false positive rate as compare to use of CCTA alone.

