In order to assess the primary endpoint of comparison of event rates for patients treated with CCTA and FFR-CT, we will perform a retrospective chart review of Invasive Coronary Angiograms performed at Lenox Hill Hospital from 2014 to 2018. We will specifically review Cardiac Catheterization reports to screen patients and record data for cases where the indication for Catheterization was (1) Positive stress test and/or (2) Positive CCTA. Based on the catheterization report we will determine whether the patient had obstructive coronary artery disease with/without flow limitation, in the same manner and following the same definitions as those used to categorize level of obstruction in subjects enrolled in the prospective cohort of the study. This data will be used as comparison/control group to assess trends and rates of invasive coronary catheterization when no intervention is necessary, in cases where CCTA and/or stress test without CT-FFR was used to determine the need for cardiac catheterization. Only the minimum amount of data required for a robust comparison of event rates will be collected.

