14.1 Sample Size Determination

Based on data from Stony Brook and confidential data HeartFlow reported from providers who have been using CT-FFR in a similar manner as we propose for this study, we estimated that about 60% of stable chest pain patients who had CCTA were diagnosed with coronary stenosis of 30% to 90% and received CT-FFR. Of these patients, about 35% had an ICA test, and 14% of those had a negative ICA test result (i.e. the false-positive rate of CCTA+CT-FFR was 14%). A sample of 121 patients who received ICA will yield 80% statistical power of detecting a 60% reduction in the false-positive rate (from 14% to 6%), based on a two-sided one sample Chi-square test with 0.05 significance level. Assuming a similar prevalence of flow-limiting obstructive CAD and assuming that similar proportions of stable chest pain patients who had CCTA will receive CCT-FFR and then ICA, 576 stable chest pain patients who had CCTA need to be complete the clinical trial. In order to target 576 subjects completing the trial, we estimate that number of patients, it will be necessary to 594, because 18 patients who enrolled were screen failures.

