For Aim 3, a survival analysis regression model will be carried out to determine which risk factors are associated with “time-to-return visit”. Proposed factors will include age, sex, race, diabetes, hyperlipidemia, hypertension, active smoking and smoking history, family history of premature heart disease, obesity, and the number of cardiac risk factors present. In addition we will consider adding whether the admission was surgical or medical, and the MS or AP DRG case weight as a measure of severity.

Statistical Methods

Descriptive statistics (n, mean, median, standard deviation, IQR, frequencies and percentages) will be used to describe the demographic and clinical characteristics of the whole sample.

For Aim 1, sensitivity, specificity, PPV, and NPV will be computed using the ICA result as the ‘true’ flow-limiting obstructive CAD status and the CCTA+CT-FFR test result as the ‘test’ status. Exact binomial 95% confidence intervals will be computed.

For Aim 2, inter- and intra-observer reliability for the CCTA and CCTA+CT-FFR tests will be assessed using Cohen’s Kappa coefficient. Dependent Kappa coefficients will be compared using a method developed by Donner et al .

For Aim 3, a survival analysis regression model will be carried out to determine which risk factors are associated with “time-to-return visit”. Proposed factors will include age, sex, race, diabetes, hyperlipidemia, hypertension, active smoking and smoking history, family

history of premature heart disease, obesity, and the number of cardiac risk factors present. In addition we will consider adding whether the admission was surgical or medical, and the MS or AP DRG case weight as a measure of severity.

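### The 90-day hazard model planned for the primary event has no comparable risk set in controls selected at ICA; the per-ICA cohort comparison is missing from 14.2; and the 80% power in 14.1 is for a one-sample test

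*Combined protocol and SAP*

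**What the plan says.** Section 6.2 defines the primary event as an ICA performed when no intervention is needed, and states "we expect to compare event rates for patients treated with CCTA and FFR-CT, using t-tests and a multivariate, risk adjusted 90 day hazard model". The Study Summary, under Statistical Methodology, gives the same plan: "using t-tests and a multivariate, risk adjusted 90 day hazard model with 95% confidence interval". Neither place states a denominator or a time origin.

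Sections 6.1, 7.4 and 9 describe the comparison group: a chart review of ICAs done at the hospital from 2014 to 2018, limited to "cases where the indication for Catheterization was (1) Positive stress test and/or (2) Positive CCTA". Section 9 names three identifiers to be collected for controls: name, procedure date and age. Study patients enter at the outpatient CCTA visit (6.1, 9.1) and are contacted 90 to 120 days after it (8.6).

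Section 14.1 reports that "14% of those had a negative ICA test result (i.e. the false-positive rate of CCTA+CT-FFR was 14"%. It continues "A sample of 121 patients who received ICA will yield 80% statistical power" to detect a fall from 14% to 6%, "based on a two-sided one sample Chi-square test with 0.05 significance level".

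Section 14.2 has three aims: accuracy of the study test against ICA, reader reliability, and predictors of a return visit within 90 days. Its only time-to-event analysis is in Aim 3, where "a survival analysis regression model will be carried out to determine which risk factors are associated with" time to return visit. The retrospective cohort is not mentioned.

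**The concern.** A hazard model needs people who are at risk and have not yet had the event, followed from a common starting point. Controls found through catheterization reports do not provide that, so the risk-adjusted part of the primary analysis has no usable form for them. Section 14.2 supplies no substitute, which leaves the denominator, the test and any adjustment to be chosen after the data are seen.

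Two consequences follow. The stated power belongs to a different test from the comparison that 6.1 and 6.2 describe. And the conclusion could be worded too broadly: a comparison among ICA recipients shows how often an ICA finds disease that needs treatment, whereas sections 10 and 11 anticipate less use of diagnostic catheterization. A lower negative fraction among ICAs can occur whether the number of ICAs falls, stays the same or rises.

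**Working it through.** **1. Time origin and risk set.**
- Clock starts at ICA: the event is decided at that ICA, so every control has zero time at risk.
- Clock starts at the earlier stress test or CCTA: controls then have an interval up to ICA, but everyone who was tested and never had an ICA is missing. Study patients who never reach ICA are included. The risk sets still differ, and no index-test date is named among the control data.

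**2. Which denominator can be shared.** From 14.1, the share of CCTA patients who reach ICA is 0.60 × 0.35 = 0.21. Rates of 14% and 6% per ICA therefore equal 0.21 × 14% = 2.9% and 0.21 × 6% = 1.3% per CCTA patient. Controls have no CCTA-level denominator, so only the per-ICA rate can be compared. Section 14.1 uses it. In 14.2, a positive test means that ICA is required, so 1 − PPV implies it for the study cohort.

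**3. The plan's own power.** One-sample test, normal approximation, p0 = 0.14, p1 = 0.06, two-sided 0.05:

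n = [1.960 × √(0.14 × 0.86) + 0.842 × √(0.06 × 0.94)]² / 0.08² = 120.99, so 121. Power at 121 is 0.800, and 121 / 0.21 = 576. The figures in 14.1 reproduce.

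**4. Power when the control rate is sampled.** Pooled-variance z test with 121 study ICAs and r × 121 control ICAs:

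power = Φ{ [|pC − pS| − 1.960 × √(p̄(1 − p̄)(1/121 + 1/(121r)))] / √(pS(1 − pS)/121 + pC(1 − pC)/(121r)) }

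where p̄ is the rate pooled over both cohorts. Example, 14% vs 6% at r = 1: p̄ = 0.10, the two standard errors are 0.0386 and 0.0382, and Φ[(0.08 − 1.960 × 0.0386)/0.0382] = Φ(0.115) = 0.546.

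The documents give no number of control ICAs, so the ratios are assumptions.

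| Meaning of 14% | Control rate vs study rate | 1:1 | 3:1 | 10:1 |
|---|---|---|---|---|
| Control rate | 14% vs 6% | 54.6% | 67.9% | 75.7% |
| CCTA+CT-FFR rate | 30.4% vs 14% | 87.2% | 96.8% | 99.0% |
| CCTA+CT-FFR rate | 25% (assumed) vs 14% | 58.0% | 73.5% | 81.3% |

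The 30.4% is 0.14 / (1 − 0.54), taken from the vendor report in 3.4 that routine CT-FFR use "has resulted in a 54% reduction in false positive rate as compare to use of CCTA alone". Applying it to these controls is an assumption. In the first row, power is 77.8% at 20:1 and 79.1% at 50:1, so it approaches the 80% in 14.1 only as the control rate becomes almost known.

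**The case against.** Several points on the other side stand.

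- *Time at risk.* Section 6.2 gives no origin, so it is too simple to say that controls have no time at risk under any reading. From an earlier test, time does exist. What remains is the missing tested-but-not-catheterized group, and that is enough to rule the model out here.
- *Denominator.* Section 14.1 and the PPV in 14.2 point to ICA recipients, and the comparison is announced elsewhere in the same document. But neither place defines the rate for both cohorts, and 14.2 gives no analysis of it.
- *The t-test.* A reader might infer that it is invalid. On 0/1 data it is not a problem: with 7/121 vs 17/121, p = 0.0316 by t-test and 0.0315 by two-proportion z test.
- *Power.* A reader might infer that the trial is underpowered or must enrol more. The documents do not support that. The label on 14% is unsettled, the number of controls is not given, and the results above run from 55% to 99%.
- *Adjustment.* A reader might infer that adjustment is impossible because only 121 × 0.06 = 7.3 study events are expected. A pooled model uses both cohorts, about 7.3 + 16.9 = 24 events at 1:1 under 14% vs 6% and more with more controls, and age is already collected for controls.
- *Avoided catheterizations.* A reader might infer that only controls selected at CCTA could address these. As 6.1 is written, patients with 30% to 100% stenosis receive both stress MPI and CT-FFR, which could allow a within-patient comparison of referral. Sections 8.3 and 9 restrict stress MPI. That conflict and the 70%/71% boundary are separate matters and are not part of this point.

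**Conclusion.** The point holds and should be fixed before analysis. The hazard model attached to the primary event has no comparable risk set for controls chosen because they had an ICA. The comparison that can be made, a per-ICA proportion in two cohorts, is not defined in 6.2 or analysed in 14.2. This part needs no numerical assumption.

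On power, the established fault is a mismatch: 80% is correct for a one-sample test against a fixed 14% and does not carry over to a sampled control group. Whether actual power is below 80% is not established. If 14% is the control rate, power is 55% to 76% over the assumed ratios from 1:1 to 10:1. If it is the CCTA+CT-FFR rate, as 14.1 labels it, power at 1:1 is 87% for an assumed control rate of 30.4% and 58% for 25%.

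**What to change.** 1. In the Study Summary, 6.2 and 14.2, define the primary measure as the proportion of ICAs with no flow-limiting disease or intervention, among ICA recipients in both cohorts. Use one definition that catheterization reports can support. The FFR cut-off is ≤ 0.8 in 6.1 and < 0.8 in 14.2; these must be reconciled.
2. Drop the hazard model for this endpoint, or place it under Aim 3 if it was meant for return visits. Add to 14.2 a two-sample comparison of proportions, giving the difference with a 95% confidence interval. Any risk adjustment should be by logistic regression on prespecified covariates recorded in both cohorts.
3. Report controls by indication, positive CCTA versus stress test alone, because the selection rule admits controls who had no CCTA.
4. In 14.1, state which cohort the 14% belongs to, and restate power for the two-sample comparison with the planned number of control ICAs. This does not require added enrolment.
5. Word the conclusion from this comparison as ICA yield, not as fewer catheterizations.

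Cost: mostly changes of wording. Adjustment may need some extra chart abstraction for controls; beyond age, the documents do not say which covariates are collected. The headline claim becomes narrower, and the stated power may be lower.

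### Section 6.2 names unspecified t-tests for a yes/no primary event while 14.1 sizes the trial on a chi-square test; some forms of t-test would raise the type I error in CT-FFR's favour, so one test of proportions should be named

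*Combined protocol and SAP*

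**What the plan says.** Section 6.2 sets the primary event with the words "Defining an event as performance of ICA when no intervention is necessary". For each ICA that is either true or false. The analysis follows in the same sentence: "we expect to compare event rates for patients treated with CCTA and FFR-CT, using t-tests and a multivariate, risk adjusted 90 day hazard model". The Study Summary (Statistical Methodology) repeats it: "we expect to compare event rates for patients treated with CCTA and FFR-CT, using t-tests". Neither place says whether the t-test is pooled, unequal-variance or one-sample, and neither states a denominator.

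Section 14.1 uses another test. The sample size is "based on a two-sided one sample Chi-square test with 0.05 significance level", for a fall in the proportion of negative ICAs from 14% to 6%, and it concludes: "A sample of 121 patients who received ICA will yield 80% statistical power".

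Section 14.2 covers diagnostic accuracy, reader agreement and return visits. It gives no test for the comparison in 6.2. Sections 6.1, 7.4 and 9 add the control group: ICAs done at the same hospital from 2014 to 2018 because of a positive stress test and/or a positive CCTA. Its size is not given.

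**The concern.** The only unadjusted test named for the primary endpoint is a t-test of unstated form. It is not the test used for sizing, and nothing in the plan reconciles the two.

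The form matters because of where the variance comes from. The chi-square test uses the null rate or the rate pooled over both groups. A one-sample t-test, and a Welch test against a large control group, take the variance mainly from the CT-FFR group's own observed rate. For a rate well below 50%, a group that is low by chance then also gets a standard error that is too small. Chance results in favour of CT-FFR are declared significant too often, and chance results against it too rarely. With the form left open, the analyst could also choose it after seeing the data.

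**Working it through.** **Inputs.** From 14.1: 121 ICAs with CT-FFR, rates of 14% and 6%, two-sided 0.05, 80% power, and the shares 60% and 35%. Assumed, because the documents do not give it: a control group of 60 to 2,000 ICAs. The count of events per ICA is inferred from 14.1 and from the ICA-only control group.

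**Step 1: the plan's own figure.** One-sample test of a proportion:

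n = [1.960 × √(0.14 × 0.86) + 0.842 × √(0.06 × 0.94)]² / (0.14 − 0.06)² = (0.680 + 0.200)² / 0.0064 = 120.99, so 121.

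121 / (0.60 × 0.35) = 576. Both stated numbers reproduce, so 14.1 did use a one-sample chi-square test against a fixed 14%.

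**Step 2: one-sample tests at n = 121, true rate 14%.** The chi-square standard error is √(0.14 × 0.86 / 121) = 0.0315. The t-test standard error is √(p̂(1 − p̂) / 120), with p̂ the observed rate.

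| Events | p̂ | chi-square z (limit −1.96) | one-sample t (limit −1.98) |
|---|---|---|---|
| 9 | 7.4% | −2.08 | −2.74 |
| 10 | 8.3% | −1.82 | −2.28 |
| 11 | 9.1% | −1.56 | −1.87 |

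Chi-square rejects in CT-FFR's favour at 9 or fewer events, the t-test at 10 or fewer. From Binomial(121, 0.14), P(X ≤ 9) = 1.95% and P(X ≤ 10) = 3.91%. The opposite tail is 2.83% for chi-square and 1.61% for the t-test. The totals are 4.78% and 5.53% (tails summed before rounding).

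**Step 3: two-group tests, no true difference.** For every pair of outcomes from Binomial(121, p) and Binomial(n₂, p), each test was applied and the probabilities of rejection were summed. This is exact, not simulated. Chi-square is without continuity correction.

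At p = 14%:

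| Controls n₂ | chi-square, favours CT-FFR | Welch, favours CT-FFR | chi-square, total | Welch, total |
|---|---|---|---|---|
| 60 | 2.95% | 1.59% | 5.22% | 5.06% |
| 121 | 2.52% | 2.52% | 5.04% | 5.04% |
| 242 | 2.34% | 3.30% | 5.03% | 5.25% |
| 500 | 2.12% | 3.78% | 4.98% | 5.32% |
| 1,000 | 2.01% | 4.16% | 4.90% | 5.58% |
| 2,000 | 1.99% | 4.33% | 4.92% | 5.68% |

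The pooled t-test equals chi-square to two decimals in both tails for 121 controls or more.

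**Step 4: a higher base rate.** Section 14.1 labels the 14% as the rate with CCTA plus CT-FFR. If that is right, the 54% reduction reported in 3.4 implies a rate without CT-FFR of 0.14 / (1 − 0.54) = 30.4%. At p = 30%, with 242 to 2,000 controls, the Welch tail in CT-FFR's favour is 2.77% to 3.21%, against 2.43% to 2.31% for chi-square. At 50% the tests are practically the same.

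**Step 5: what 14.1 does not cover.** Comparing 14% with 6% between two groups of equal size, at the same error and power, needs [1.960 × √(2 × 0.10 × 0.90) + 0.842 × √(0.14 × 0.86 + 0.06 × 0.94)]² / 0.0064 = (0.832 + 0.354)² / 0.0064, about 220 per group. The 121 is enough only if the comparison rate is known without error.

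**The case against.** The strongest reply is that a t-test on 0/1 data is practically a chi-square test. For the pooled form this is correct, and pooled is a natural reading of the text. The one-sample form fits 6.2 poorly, because 6.2 compares two groups of patients. The Welch effect needs a control group well above 121. Section 6.1 keeps only ICAs with two kinds of indication, so five years of records need not give thousands. All of this stands, and it limits the point to a condition: the error is inflated only under some forms of the t-test and some control sizes.

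A reader might infer that t-tests in general double the chance of a false claim for CT-FFR. The documents do not support that. The one-sample tail doubles relative to chi-square (3.91% against 1.95%), but partly because the chi-square tail is itself below nominal; against 2.5% the ratio is about 1.6. For Welch, doubling needs about 1,000 controls and a rate near 14%. Section 14.1 promises two-sided 0.05, not 2.5% in each tail, and the total moves little.

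A reader might also infer that the reported confidence interval is wrong. In 6.2 the 95% interval is attached to the hazard model; no t-test interval is specified, and coverage was not calculated here.

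What the reply does not answer is that the form is unstated. Ten events in 121 against a fixed 14% is significant under one reading and not under another.

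**Conclusion.** The point holds as a minor one. The plan names an unspecified t-test for a yes/no primary event, sizes the trial on a chi-square test, and does not reconcile them. At worst, within the range examined at a 14% rate, the type I error in CT-FFR's favour is about 4% instead of the nominal 2.5%, while total two-sided error rises by less than one percentage point (largest rise: 5.68% against 4.92%). The size rests on three things that the documents leave open: the form of the t-test, the number of control ICAs, and whether 14% is the right rate for the null case. Under a pooled t-test, or with equal groups, the effect is nil.

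**What to change.** In 6.2 and the Study Summary, replace the t-tests by a two-sided Pearson (score) chi-square test at 0.05. It should compare the proportion of ICAs with no intervention necessary between the CT-FFR cohort and the retrospective control cohort, with a score-based 95% confidence interval for the difference. Name it as the unadjusted primary test, and state how it ranks against the risk-adjusted model in the same sentence. Stating the proportion in this way also fixes the denominator.

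In 14.1, add that the one-sample calculation treats the comparison rate as fixed, so its 80% power does not describe this two-group test. Give the expected number of control ICAs and the power that follows from it.

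Cost: one sentence in two places and a short addition to 14.1; no further data or patients. The downside is that a borderline result may become slightly less favourable to CT-FFR.

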8.3 Method for Assigning Subjects to Treatment Groups

This is not a randomized study. Treatment assignments will follow the clinical protocol.

Once the CCTA results are interpreted by the physician, the physician will order CT-FFR exams for patients whose level of stenosis by CCTA standards is 30% to 100%.

If CT-FFR is positive patients will be referred for Cardiac Catheterization and invasive FFR.

If CT-FFR is negative, and level of obstruction is 30 to 49% by CCTA standards, patients will be referred to optimal medical care.

If CT-FFR is negative and level of obstruction is 50% to 70% by CCTA standards, patient will be referred for stress MPI. If stress MPI is positive patients will be referred for Cardiac Cath and invasive FFR. If stress MPI is negative, patients will be referred to optimal medical care.

If the patient has had a stress MPI within one year of the CCTA exam and the CCTA exam result is 50% to 70% obstructive, the physician will rely on the prior stress testing result, rather than repeating the stress test. If the stress testing results was negative, the patient will be referred to optimal medical care. If, in the investigator's opinion, the results indicate that the patient is at increased risk of obstructive disease, when considered with the CCTA findings, the patient will be referred to Cardiac Cath and Invasive FFR.

If CT-FFR is negative and level of obstruction is 70% to 100% by CCTA standard, patient will be referred to Cardiac Cath and Invasive FFR.

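### Section 6.2 tests one primary null with both t-tests and a risk-adjusted model against non-randomised controls, and never says which result decides

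*Combined protocol and SAP*

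**What the plan says.** Section 6.2 (Primary Study Endpoints) sets one event and one comparison: "Defining an event as performance of ICA when no intervention is necessary, we expect to compare event rates for patients treated with CCTA and FFR-CT". The methods follow: "using t-tests and a multivariate, risk adjusted 90 day hazard model with 95% confidence interval". A single null covers both: "Our null hypothesis is that outcomes will not vary regardless of which testing is used to assess" obstructive disease. The Study Summary names the same pair of methods. The alternative is worded as "evaluation with FFR-CT as oppose to CCTA will change the event rate" in 6.2 and as "evaluation with FFR-CT as oppose to CCTA alone will reduce the event rate" in the Study Summary.

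Section 6.2 ends with a further item: "We will also correlate noninvasive and invasive FFR studies". It carries no hypothesis, threshold or stated role.

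Section 14.1 sizes the study "based on a two-sided one sample Chi-square test with 0.05 significance level". Section 14.2 covers diagnostic accuracy, kappa reliability and return visits. It has no between-group analysis of the primary event, and its only regression is for return visits. Section 14.3 mentions adjustment only for subjects who could not finish part of the study.

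On the design, section 8.3 says "This is not a randomized study". Sections 6.1, 7.4 and 9 take the controls from catheterisation charts of 2014 to 2018.

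**The concern.** The word 'and' joins the two methods under a shared null. The plan does not say which is primary, whether both must be significant, or what is concluded if they disagree. An analyst could follow it to the letter and report either result as the primary finding.

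In a randomised trial this would do limited harm, because both analyses would address the same contrast in comparable groups. Here the groups are assembled differently. Section 7.2 excludes enrolled patients with earlier stenting or bypass surgery, eGFR below 50 or BMI above 50; the chart-review text states none of these exclusions. Controls qualify on a positive stress test and/or a positive CCTA, so on that wording some could enter on a stress test alone (section 7.5 does describe them as having had CCTA). Every enrolled patient enters through CCTA. An unadjusted comparison mixes any effect of CT-FFR with these differences, and the plan lets it carry the primary claim.

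**Working it through.** **1. The plan's own figure.** Inputs from 14.1: p0 = 0.14, p1 = 0.06, two-sided 0.05, 80% power.

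n = [1.960 × √(0.14 × 0.86) + 0.842 × √(0.06 × 0.94)]² / (0.14 − 0.06)² = 120.99, so 121 angiograms. Then 121 / (0.60 × 0.35) = 576.2, so 576 completers.

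Both figures reproduce. They belong to a one-sample test against a fixed 14%, which is neither of the analyses in 6.2.

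**2. The same rates as a two-group comparison.** With a pooled normal approximation, 14% v 6% needs 220 per group for 80% power. With 121 prospective angiograms, power is 54.6% with 121 controls, 63.6% with 242, 67.9% with 363 and 75.7% with 1,210. The documents do not give the number of controls.

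**3. How far the two analyses part company.** Trials were simulated with a pooled t-test on the binary event and a logistic model adjusted for one covariate, the latter standing in for the unspecified risk-adjusted model. Both used two-sided 0.05. Assumptions, none from the documents: covariate log-odds slope -0.7 per SD; imbalance of 0, 0.25 or 0.5 SD in the direction that favours CT-FFR; 121 prospective and 121 or 363 control angiograms; control event rate near 14%. The alternative uses odds ratio (0.06/0.94)/(0.14/0.86) = 0.39. There were 3,000 trials per setting.

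| Imbalance (SD) | Controls | Null: t-test | Null: adjusted | Null: either | Null: differ | Alternative: adjusted power | Alternative: differ |
|---|---|---|---|---|---|---|---|
| 0 | 121 | 0.046 | 0.041 | 0.052 | 0.017 | 0.507 | 0.067 |
| 0 | 363 | 0.049 | 0.044 | 0.058 | 0.024 | 0.636 | 0.078 |
| 0.25 | 121 | 0.073 | 0.052 | 0.091 | 0.058 | 0.466 | 0.172 |
| 0.25 | 363 | 0.078 | 0.048 | 0.100 | 0.075 | 0.594 | 0.190 |
| 0.5 | 121 | 0.135 | 0.048 | 0.155 | 0.127 | 0.404 | 0.338 |
| 0.5 | 363 | 0.157 | 0.043 | 0.181 | 0.162 | 0.524 | 0.347 |

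'Differ' means that one analysis is significant and the other is not.

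**4. Imbalance in either direction.** A second set used intercept -1.95, the same slope, imbalance of 0 or ±0.3 SD, 121, 300 or 500 controls, and odds ratio 1 or 0.4.

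- Correlation of the two statistics: about 0.92 to 0.97.
- Null, balanced: either significant in about 5% to 6%.
- Null, 0.3 SD imbalance: either significant in about 9% to 14%; adjusted test alone about 4% to 6%.
- Null, false results favouring CT-FFR from either test: about 7% to 9% when the imbalance favours it, about 2% when it goes against. Without selection, 2.5% would be expected in that direction.
- Odds ratio 0.4, 0.3 SD imbalance: the tests differ on significance in about 18% to 29%.
- Odds ratio 0.4, power of the adjusted test: about 45% to 77% overall, about 52% to 67% when balanced.
- Both tests significant in opposite directions: never.

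**The case against.** An unadjusted comparison followed by an adjusted model is a common pairing, and the 95% confidence interval in 6.2 is attached to the model, so a sympathetic reader could take the model as the inferential analysis. The document also never uses the word 'unadjusted'; that is only the natural reading of t-tests placed beside a risk-adjusted model. These points make the intended answer easier to guess. They do not state it, and the shared null leaves the t-test free to decide.

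Three stronger readings are tempting and are not supported.

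- A reader might infer that the plan can yield opposite conclusions. The disagreement is between significant and not significant; contradictory directions did not occur in the simulated trials.
- A reader might add 0.05 + 0.05 and infer an error rate near 10% from multiplicity alone. The two tests use the same data and are so highly correlated that the balanced figure is about 5% to 6%.
- A reader might count the FFR correlation and the chi-square test as third and fourth competing tests. The correlation does not address the event-rate null, and 14.1 names the chi-square test only for sizing.

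It is also fair that the upper end of the 9% to 14% range comes from imbalance that makes CT-FFR look worse, which would not support a favourable claim.

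**Conclusion.** The concern holds for the pair of t-tests and risk-adjusted model: one null, two analyses, no deciding rule in 6.2, the Study Summary or section 14. The harm is less extra alpha than a free choice between an answer exposed to confounding and an adjusted one. How large it is depends on control numbers, covariate strength and imbalance, none of which the documents give, so the simulated ranges illustrate the problem and are not predictions for this study. Adjustment recovers the nominal error rate in these simulations because the one confounder is measured; unmeasured differences would remain. The gap is separate from whether a t-test or a hazard model suits this event: with two better-chosen tests the plan would still not say which decides. It should be repaired before the comparison is run.

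**What to change.** In 6.2 and the Study Summary, state that the primary conclusion rests on the risk-adjusted comparison of the CT-FFR cohort with the chart-review controls at two-sided alpha 0.05, and that the unadjusted comparison is supportive and cannot by itself establish the primary result. Word the alternative the same way in both places.

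Name the model and a short prespecified covariate list; an unspecified adjusted model would only move the choice elsewhere. The covariates in 14.2 are proposed for return visits (Aim 3), so the primary analysis needs its own. The list must be short: at the planning rates, 121 × 0.06 + 121 × 0.14 gives about 24 events with 121 controls.

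Add those covariates to the control chart review. Section 9 limits that review to the minimum data needed, and the only items it names are the identifiers: name, procedure date and age. Label the FFR correlation in 6.2 as secondary or descriptive.

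Cost: some protocol wording, a few baseline items abstracted per control, and the loss of any claim from a significant unadjusted result alone. Adjustment costs almost no power when the groups are balanced (adjusted v unadjusted 0.507 v 0.506 with 121 controls, 0.636 v 0.643 with 363). The two-group comparison is nevertheless well short of 80% under these assumptions, so section 14.1 should give the power of the named primary analysis with a stated number of controls.
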